Vital signs	X	X	X	X	X	X	X	X	X	X	X	X	Vital signs include pulse rate, blood pressure, and temperature. Vitals should be measured after participant has been sitting for at least 5 minutes. Vital signs are measured prior to and within 30 minutes after infusion for clinical management, and not recorded in the CRF.
Weight (for aducanumab participants only)	X	X	X	X	X	X	X	X	X				Weight is measured prior to dosing with aducanumab only and is not recorded in the CRF.

	Open-Label Treatment											Short-term Follow-up	Comments
Visit Number	12	13	14	15	16	17	18	19	20	21	ET	801-804^	^Visit 801 to 804 may be used for return to baseline ADA monitoring and other safety assessments at discretion of the sponsor and may be requested within the time period listed.
Weeks relative to first infusion	40	44	48	52	56	60	64	68	72	76	-	84-120	
Visit interval tolerance (days)	±7	±7	±7	±7	±7	±7	±7	±7	±7	±7	-	±14	
MRI		X											MRI at V13 is to be performed and reviewed prior to V13 infusion. The MRI should occur at least 14 days after infusion at V12 is administered, and may occur outside of the visit windows. Unscheduled MRIs may be performed at the discretion of investigator, for example, if titration is delayed due to temporary suspension of infusions.
Florbetapir F18 PET scan				X						X	X		Collect at ET only if ET occurs at 3 or more IP infusions after the last florbetapir F18 PET scan.
Laboratory Tests and Sample Collections	In the event that study intervention is delayed, all laboratory collections should occur on the same day as study intervention infusion - and should be collected prior to infusion.												
Hematology and clinical chemistry				X						X	X		Collect prior to infusion.
PK sample				X						X	X	X	Collect prior to infusion. Predose collections may be collected from the IV site prior to the infusion.
Immunogenicity (ADA) samples				X						X	X	X	Collect prior to infusion.

	Open-Label Treatment											Short-term Follow-up	Comments
Visit Number	12	13	14	15	16	17	18	19	20	21	ET	801-804^	^Visit 801 to 804 may be used for return to baseline ADA monitoring and other safety assessments at discretion of the sponsor and may be requested within the time period listed.
Weeks relative to first infusion	40	44	48	52	56	60	64	68	72	76	-	84-120	
Visit interval tolerance (days)	±7	±7	±7	±7	±7	±7	±7	±7	±7	±7	-	±14	
Stored Samples													
Exploratory biomarker samples				X						X	X		Collect prior to infusion.

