4.1. Overall Design

Study AACN is a multicenter, randomized, open-label, head-to-head, Phase 3 study of donanemab compared to aducanumab in participants with early symptomatic AD.

Participants who meet entry criteria will be randomized in a 1:1 ratio to 1 of the following treatment groups:

- donanemab: 700 mg IV Q4W for first 3 doses and then 1400 mg IV Q4W
- aducanumab: refer to PI/routine clinical practice

The maximum total duration of study participation for each participant, including screening and the post-treatment follow-up periods, is up to 127 weeks:

- Lead-In: any time prior to complete screening
- Complete Screening: up to 7 weeks
- Open-label study period: 76 weeks
- Follow-Up: up to 44 weeks

The maximum duration of treatment is 72 weeks.

Scheduled Reduction of Donanemab

Participants randomized to donanemab whose amyloid plaque reduction as measured by florbetapir F18 PET scans at Visit 8 (Week 24) or Visit 15 (Week 52) meets criteria will stop donanemab infusions but continue all other assessments for the remaining duration of the open-label period and short-term follow-up period. These dose reduction rules are defined by the sponsor.

Participants randomized to aducanumab will continue monthly infusions throughout the open-label period, regardless of amyloid plaque reduction on florbetapir F18 PET scans.

Change in amyloid burden (as assessed with florbetapir F18 PET by personnel blinded to treatment allocation) will be compared in donanemab and aducanumab-treated participants.

Participant randomization will be stratified by amyloid burden and ApoE ϵ 4 status (noncarrier/heterozygous/homozygous).

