7.1. Discontinuation of Study Intervention

In rare instances, it may be necessary for a participant to permanently discontinue study intervention. If study intervention is permanently discontinued, the participant should remain in the study to be evaluated for safety and biomarker collection. See the SoA for data to be collected at the time of discontinuation of study intervention and follow-up and for any further evaluations that need to be completed.

A participant should be permanently discontinued from study intervention if

- the participant becomes pregnant during the study
- by request of the participant or participant's designee (for example, legal guardian)
- based on a specific AE profile, the Medical Monitor, or the study sponsor physician/scientist, in discussions with the Principal Investigator
- incorrect enrollment
- severe noncompliance to the study protocol in the judgment of the investigator
- systemic hypersensitivity reaction suspicious for an anaphylactic reaction or angioedema
- participant requires an excluded therapeutic agent
- based on investigator clinical judgment
- participants answered 'yes' to Question 4 or 5 on the 'Suicidal Ideation' portion of the C-SSRS, or
- participants answered 'yes' to any of the suicide-related behaviors on the Suicidal Behavior portion of the C-SSRS.
 - a psychiatrist or appropriately trained professional may assist in the decision to discontinue the participant for C-SSRS responses.

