7.2. Participant Discontinuation/Withdrawal from the Study

A participant may withdraw from the study

- at any time at the participant's own request
- at the request of the participant's designee (for example, parents or legal guardian)
- at the discretion of the investigator for safety, behavioral, compliance, or administrative reasons
- if enrollment in any other clinical study involving an investigational product or enrollment in any other type of medical research judged not to be scientifically or medically compatible with this study, or
- if the participant, for any reason, requires treatment with another therapeutic agent that has been demonstrated to be effective for treatment of the study indication, discontinuation from the study occurs prior to introduction of the new agent.

Discontinuation is expected to be uncommon.

At the time of discontinuing from the study, if possible, an early discontinuation visit should be conducted, as shown in the SoA. See SoA for data to be collected at the time of study discontinuation and follow-up and for any further evaluations that need to be completed. The participant will be permanently discontinued from both the study intervention and the study at that time.

If the participant withdraws consent for disclosure of future information, the sponsor may retain and continue to use any data collected before such a withdrawal of consent. If a participant withdraws from the study, he/she may request destruction of any samples taken and not tested, and the investigator must document this in the site study records.

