9.5. Sample Size Determination

Approximately 200 participants will be enrolled and randomized in a 1:1 ratio to the 2 treatment regimens (donanemab and aducanumab). It is expected that approximately 180 participants will complete 6-month florbetapir F18 PET scans (approximately 90 per treatment regimen). It is

further anticipated that approximately 50% of participants randomized will belong to the intermediate tau subpopulation.

This sample size will provide at least 98% power to demonstrate that donanemab is superior to aducanumab in achieving complete amyloid brain plaque clearance individually at 6 months in the overall population and the intermediate tau subpopulation. Power estimates were obtained using specific contrasts for the 6-month time point of treatment by time interaction effect within the framework of generalized linear mixed effect model assuming a logit link.

The assumptions for this power calculation are that 35.7%, 50.1%, and 54.6% of donanemab treated participants reach complete brain amyloid clearance at 6 months, 12 months, and 18 months, respectively. The corresponding complete brain amyloid clearance percentages for aducanumab treated participants are assumed to be 3.0%, 22.8%, and 27.8%, respectively. The simulation for the power calculation and sample size determination was carried out in SAS Enterprise Guide Version 7.15 and all sample size estimates were obtained assuming a 2-sided significance level of 0.05.

10. Supporting Documentation and Operational Considerations

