4.4.3. Sensitivity Analyses

A last-observation-carried-forward (LOCF) analysis for complete amyloid plaque clearance will be conducted. For participants without PET scan results at either 12 or 18 months, the centiloid measurement from their last available post-baseline PET scan will be used to determine complete amyloid plaque clearance for the missing assessments.

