4.5.1.3. Sensitivity Analyses

Observed values for mean changes in centiloid values will be reported for 6-, 12-, and 18- month PET scans. Additionally, a last-observation-carried-forward (LOCF) mean change analysis in centiloid values will be reported.

Time to plaque clearance will also be analyzed using a Cox proportional-hazards model with the treatment group as fixed effect variable of interest, and APOE e4 genotype, baseline amyloid levels, and baseline age as covariates.

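### Does tying the early-termination amyloid scan to an infusion count leave a damaging gap for donanemab participants stopped on a PET result?

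*Protocol*

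**What the plan says.** Protocol 1.3, Visits 12 through 21 and Follow-Up, attaches this condition to the ET florbetapir scan: "Collect at ET only if ET occurs at 3 or more IP infusions after the last florbetapir F18 PET scan". It gives no elapsed-time alternative. The other ET samples (chemistry, PK, antibodies, exploratory biomarkers) carry no infusion count. The definition of investigational product in Protocol Appendix 10 includes reference products, so aducanumab infusions count.

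Under Protocol 4.1, a donanemab participant whose Week 24 or Week 52 scan "meets criteria will stop donanemab infusions but continue all other assessments for the remaining duration of the open-label period and short-term follow-up period". For the comparator: "Participants randomized to aducanumab will continue monthly infusions throughout the open-label period, regardless of amyloid plaque reduction on florbetapir F18 PET scans". Protocol 7.1 says of anyone permanently off drug that "the participant should remain in the study to be evaluated for safety and biomarker collection", and Protocol 7.2 adds: "Discontinuation is expected to be uncommon".

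ET scans can enter the LOCF sensitivity analyses. For 12- and 18-month clearance, SAP 4.4.3 says that "the centiloid measurement from their last available post-baseline PET scan will be used to determine complete amyloid plaque clearance for the missing assessments". For mean change, SAP 4.5.1.3 says that "a last-observation-carried-forward (LOCF) mean change analysis in centiloid values will be reported". The SAP does not say how an ET scan is assigned to an analysis visit.

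**The concern.** The trigger is worded alike for both arms but does not act alike. A donanemab participant taken off infusions because of a scan result has few or no later infusions, and so normally cannot reach three. An aducanumab participant with the same result keeps being infused and soon qualifies. After Week 24, whether a leaver gets an ET scan therefore depends on treatment arm and on the observed amyloid value.

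The direction matters too. A stopper who leaves before any off-drug scan has a favourable pre-stop value carried forward, so plaque return after stopping would go unseen. An aducanumab leaver still on drug can have the value updated. In an open-label superiority trial analysed by intention to treat, outcome collection that depends on exposure in a way that could favour the experimental arm deserves a check.

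**Working it through.** **When the trigger is met.** Infusions are 4-weekly and post-baseline scans fall at Weeks 24, 52 and 76. For someone still infused, the third infusion after the Week 24 scan is at Week 32 if the Visit 8 infusion counts, or Week 36 if not. After the Week 52 scan it is at Week 60 or 64. That is 8 or 12 weeks after the scan; the Schedule does not give the order of scan and infusion within a visit. A PET stopper would reach three only if the undisclosed lag from scan to stop exceeded 8 weeks (counting the scan-visit infusion) or 12 weeks (not counting it). A Week 24 stopper has no infusions after Week 52 and cannot qualify before Week 76.

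**Inputs.** From Protocol 9.5: about 90 per arm with a 6-month scan; donanemab clearance 35.7%, 50.1% and 54.6% at 6, 12 and 18 months; aducanumab 3.0%, 22.8% and 27.8%. Assumed: stop criterion equal to clearance; the same dropout d per scan interval in both arms; exits spread evenly; Week 24 clearers stay cleared to Week 52. Dropout of 20% per interval (1 − 0.8² = 36% cumulative after Week 24) is an extreme. The plan gives no figure for ET scans to reproduce.

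**Stoppers.** By Week 24: 0.357 × 90 = 32.13. By Week 52: 0.501 × 90 = 45.09. New at Week 52: 45.09 − 32.13 = 12.96. So 32.13/45.09 = 71% of those stopped by Week 52 already have an off-drug scan.

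**Counts.** The share of exits at least 12 weeks after a scan is 16/28 = 0.571 (Weeks 24-52) and 12/24 = 0.50 (Weeks 52-76).

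- Missed scans = 32.13 × d × 0.571 + 45.09 × (1 − d) × d × 0.50
- Unchecked (no off-drug scan at all) = 32.13 × d × 0.571 + 12.96 × (1 − d) × d × 0.50

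| Dropout per interval | 5% | 10% | 20% |
|---|---|---|---|
| Missed scans | 0.92 + 1.07 = 1.99 | 1.84 + 2.03 = 3.87 | 3.67 + 3.61 = 7.28 |
| Unchecked | 0.92 + 0.31 = 1.23 | 1.84 + 0.58 = 2.42 | 3.67 + 1.04 = 4.71 |
| 12-month shift if all unchecked reverse (first term/90) | 1.0 | 2.0 | 4.1 points |
| 18-month shift if all unchecked reverse (unchecked/90) | 1.4 | 2.7 | 5.2 points |

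Planned differences are 50.1 − 22.8 = 27.3 points at 12 months and 54.6 − 27.8 = 26.8 at 18 months. If only 10% to 30% of unchecked values reversed (assumed; the documents give no rate), the 18-month shifts are 0.1-0.4, 0.3-0.8 and 0.5-1.6 points.

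Two wider readings change little. With the 8-week trigger (shares 20/28 and 16/24), unchecked leavers are 1.56, 3.07 and 5.97, and the 18-month bound is 1.7, 3.4 and 6.6 points. Counting every missed scan, including stoppers who carry forward an off-drug Week 52 value, the 12-week bound is 1.99/90, 3.87/90 and 7.28/90, or 2.2, 4.3 and 8.1 points.

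**Mean-change LOCF.** Each centiloid of average drift in the unchecked group moves the donanemab mean by 4.71/90 = 0.052 centiloids even at 20% dropout. Moving it by 5 centiloids, the SAP's own non-inferiority margin, would need 5/0.0523, or about 96 centiloids of drift.

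**Other analyses.**
- Co-primaries: the PET-based stop follows the Week 24 scan, and SAP 4.4.2 excludes anyone without a 6-month scan. No effect.
- Time to clearance (gated): the event is the first scan below 24.1 centiloids. A stopper near that threshold has already had it. An effect arises only if the stop criterion can be met without clearance.
- Mean change at 12 and 18 months (gated): among leavers, absence of an ET scan depends on arm and earlier observed centiloids, both in the repeated-measures model. A likelihood analysis is designed to accommodate such missingness.
- Clearance at 12 and 18 months: other secondary, outside the gate.

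**Cost of closing the gap.** A time-based alternative would add the 2, 4 or 7 stopper scans. If it covered all off-drug leavers, including before Week 24, it would add more. Other leavers at least 12 weeks past a scan or first infusion number 20 × 12/24 = 10 before Week 24, plus (180 − 32.13) × d × 0.571 + (180 − 45.09) × (1 − d) × d × 0.50 = 7.4, 14.5 or 27.7. If 10% to 20% of these were off drug too early to qualify (assumed), the totals are about 4-5, 6-9 or 11-15 scans. Protocol Appendix 7 plans 2 × 7.43 = 14.86 mSv of florbetapir in year one, and 23.96 mSv with flortaucipir (9.10). A third florbetapir scan gives 22.29 and 31.39 mSv. Footnote b to that table permits one such extra scan.

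**The case for a change.** The best case for changing the rule is one of principle. A trigger based on exposure sits badly with intention-to-treat and with the request that people off drug stay for biomarker collection. A leaver's scan cannot be obtained later. Durability of clearance off drug is exactly what the missing scan would have tested. The wording change would be short, and Appendix 7 already allows for the scan.

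The literal asymmetry stands, as does the point that unscanned leavers are lost for good. Three things limit it. First, stoppers who stay keep their scheduled Week 52 and Week 76 scans, so durability is measured in most of them; only early leavers are lost. Second, the trigger can be read as three infusion visits having passed, and on that reading the asymmetry disappears. Third, limiting an extra radiotracer scan to people with meaningful further exposure is a defensible choice, though that rationale is inferred and the Protocol states none.

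The silence on assigning ET scans to visits is also real, but it is missing detail rather than an error. The LOCF analyses already take the last available scan, and an analyst would set a visit window for the repeated-measures models as a matter of routine.

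**Conclusion.** No change follows. Read literally, the ET rule treats PET-stopped donanemab participants differently from anyone still infused. The gap is about 2, 4 or 7 scans at 5%, 10% or 20% dropout per interval, and about 1.2, 2.4 or 4.7 values with no off-drug check. Its demonstrated reach is the 12- and 18-month LOCF sensitivity analyses. There, even complete reversal of the unchecked values moves 18-month clearance by 1.4, 2.7 or 5.2 points, leaving at least 26.8 − 5.2 = 21.6 points of the planned difference. No primary or gated result is shown to change.

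Against that stand extra tracer scans in people leaving the study and a higher year-one dose. This is a fair trade-off between radiation and data, and the sponsor's side of it is reasonable. The conclusion rests on a stop criterion near the clearance threshold, a scan-to-stop lag of no more than 8 to 12 weeks, equal dropout in the two arms, and dropout no worse than the extreme case. The documents disclose neither the criterion nor the lag. A criterion far from clearance would alter the counts and could reach time to clearance.

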2.1. Study Rationale

Study I5T-MC-AACN (AACN) is a Phase 3, open-label, head-to-head study to evaluate the superiority of donanemab to aducanumab in reaching amyloid plaque clearance in participants with early symptomatic AD.

This strategy is based on the amyloid hypothesis of AD, which postulates that the production and deposition of A β is an early and necessary event in the pathogenesis of AD (Selkoe 2000). Clinical data supporting this hypothesis comes from the observation that parenchymal A β levels are elevated prior to the manifestation of AD symptoms, and further supported by genetic variants of AD that overproduce brain A β and genetic variants that protect against A β production (Jonsson et al. 2012; Fleisher et al. 2015). Furthermore, early in the disease, the presence of brain amyloid appears to increase the risk of conversion from MCI to AD dementia (Doraiswamy et al. 2012). These data suggest that removal of deposited amyloid and clearance of A β can result in the slowing of AD progression. Both donanemab and aducanumab have previously demonstrated the ability to reduce brain amyloid plaque burden and potentially slow clinical decline (Sevigny et al 2016; Mintun et al 2021; Aducanumab USPI, 2021). Recently, the FDA approved aducanumab for clinical use based on its ability to reduce amyloid plaque burden (Aducanumab USPI, 2021). The current study aims to evaluate the superiority of donanemab to aducanumab in reaching amyloid plaque clearance.

2.2. Background

Alzheimer's disease is an age-related neurodegenerative disorder characterized by progressive decline in cognitive function and the ability to perform activities of daily living. The amyloid hypothesis of AD postulates that the accumulation of A β is an early and necessary event in the pathogenesis of AD. This hypothesis suggests that interventions that slow the accumulation of A β plaque in the brain or increase clearance of A β may be able to slow the progression of the AD clinical syndrome. Another hallmark neuropathological lesion of AD is comprised of intraneuronal, neurofibrillary tangles consisting of tau proteins, which spread through the brain and mark disease progression (Braak and Braak 1996). The relationship between these 2 pathologies is still unclear, although the presence of both is necessary for the diagnosis of definite AD.

Converging evidence from both genetic at-risk and age at-risk cohorts suggests that the pathophysiological process of AD begins well more than a decade before the clinical stage now recognized as AD dementia, and that neurodegeneration is already apparent on MRI by the stage of MCI (Jack et al 2010). Like many disorders, AD occurs on a continuum from asymptomatic (preclinical) to MCI, and then to dementia in mild, moderate, and severe stages. Recent clinical trial results in mild-to-moderate AD dementia, as well as evidence from transgenic animal experiments, suggest that treating AD during the earlier stages could have the greatest potential benefit on the disease and inhibiting progression, particularly when considering therapies targeted at A β reduction (Doody et al. 2014; Fleisher et al. 2015; Siemers et al. 2016).

2.3. Benefit/Risk Assessment

More detailed information about the known and expected benefits and risks and reasonably expected adverse events of donanemab may be found in the IB, Participant Information Leaflet, Package Insert, or Development Safety Update Report or Summary of Product Characteristics.

More detailed information about the known and expected benefits and risks and reasonably expected adverse events of aducanumab may be found in the Participant Information Leaflet, Package Insert, or Summary of Product Characteristics.

3. Objectives, Endpoints, and Estimands

Objectives	Endpoints
Co-Primary	
To assess the superiority of donanemab versus aducanumab on complete brain amyloid plaque clearance in participants with early symptomatic AD.	Superiority of percentage of participants who reach complete amyloid plaque clearance on florbetapir F18 PET scan on donanemab versus aducanumab at 6 months.
To assess the superiority of donanemab versus aducanumab on complete brain amyloid plaque clearance in the intermediate tau subpopulation of participants with early symptomatic AD.	Superiority of percentage of participants who reach complete amyloid plaque clearance on florbetapir F18 PET scan in the intermediate tau subpopulation on donanemab versus aducanumab at 6 months.
Key Secondary	
To assess the superiority of donanemab versus aducanumab on degree of brain amyloid plaque reduction.	Superiority of mean absolute change from baseline in brain amyloid plaque on florbetapir F18 PET scan for donanemab versus aducanumab at: 
 • 6 months • 12 months, and • 18 months.
To assess the superiority of donanemab versus aducanumab in time to reach complete amyloid plaque clearance.	Time to reach complete amyloid plaque clearance on donanemab versus aducanumab.
Other Secondary	
To assess the superiority of donanemab versus aducanumab on degree of brain amyloid plaque reduction.	Superiority of mean percent change from baseline in brain amyloid plaque on florbetapir F18 PET scan for donanemab versus aducanumab at: 
 • 6 months • 12 months, and • 18 months.

Objectives	Endpoints
To assess the non-inferiority of donanemab versus aducanumab on degree of brain amyloid plaque reduction.	Non-inferiority of mean absolute change from baseline in brain amyloid plaque on florbetapir F18 PET scan at: 
 • donanemab 6 months vs aducanumab 12 months, and • donanemab 6 months vs aducanumab 18 months.
To assess the superiority of donanemab versus aducanumab on complete brain amyloid plaque clearance.	Superiority of percentage of participants who reach complete amyloid plaque clearance on florbetapir F18 PET scan on donanemab versus aducanumab at: 
 • 12 months, and • 18 months.
To assess the superiority of donanemab versus aducanumab on complete brain amyloid plaque clearance in the intermediate tau subpopulation.	Superiority of percentage of participants who reach complete amyloid plaque clearance on florbetapir F18 PET scan in the intermediate tau subpopulation on donanemab versus aducanumab at: 
 • 12 months, and • 18 months.
To assess the superiority of donanemab versus aducanumab on degree of brain amyloid plaque reduction in the intermediate tau subpopulation.	Superiority of mean absolute change from baseline in brain amyloid plaque on florbetapir F18 PET scan in the intermediate tau subpopulation for donanemab vs aducanumab at: 
 • 6 months • 12 months, and • 18 months.
To assess the superiority of donanemab versus aducanumab on degree of brain amyloid plaque reduction.	Superiority of change from baseline in brain amyloid plaque reduction on florbetapir F18 PET scan for donanemab 6 months vs aducanumab 12 months.

Objectives	Endpoints
To evaluate the safety and tolerability of donanemab vs aducanumab.	Characterization of standard safety assessments: 
 • Spontaneously reported AEs • Clinical laboratory tests • MRI (ARIA and emergent radiological findings) • Serious hypersensitivity reactions • C-SSRS

Abbreviations: AD = Alzheimer's disease; AE = adverse event; ARIA = amyloid-related imaging abnormalities; C-SSRS = Columbia Suicide-Severity Rating Scale; PET = positron emission tomography; SAP = Statistical Analysis Plan.

NOTE: Other pre-specified, non-gated endpoints not listed will be detailed in the SAP.

Estimands

Estimands are described in the SAP.

4. Study Design

